1 PROTOCOL SUMMARY

[figure not shown]
Leave blank. Text should be included under the relevant subheadings below.

1.1 SYNOPSIS

Title:	Clinical Trial of iTEST: A Blended Intervention Targeting Introspective Accuracy
Study Description:	
Objectives:	
Aim 1. Target Engagement: Evaluate in an open trial (n=60) if iTEST is acceptable and improves Introspective accuracy (IA);
 
Aim 2. Optimal Dosing: Identify the briefest duration of iTEST (8, 12, or 16 weeks) that achieves criteria.

Endpoints:	
Primary Endpoint: $\geq 75\%$ adherence, and Cohen's $d=0.5$ increase in trained IA on two tasks and in an untrained IA task.
 
Secondary Endpoints: Change in functioning based on a Cohen's $d=0.5$ increase in the Specific Level of Functioning scale score

Study Population:	People with psychotic disorders
Phase:	Ib
Description of Sites/Facilities Enrolling Participants:	UCSD; University of Texas at Dallas (Subcontracted site to UCSD)
Description of Study Intervention:	Behavioral intervention that integrates individual coaching with automated software that operates on mobile devices
Study Duration:	2 years
Participant Duration:	16 weeks

1.2 SCHEMA

This study is phase Ib (referred to an R61) of an NIH phased award (pending) wherein the goal is to determine target engagement in an open trial - the protocol here only reflects the R61 phase but the diagram below addresses the entire two phase project. If the R61 reaches its go/no go criteria, the R33 is a randomized trial that would be a different protocol and is not detailed in this document. That R33 protocol would be separate and will be submitted at a later time pending the outcome of the R61 (protocol detailed in this document).

1.3 SCHEDULE OF ACTIVITIES (SOA)

All activities listed will be administered on both sites.

	Screening Day -7 to -1	Baseline Day 0	Study Visit 2 Day 56 +/- 14 day	Study Visit 3 Day 84 +/- 14 day	Final Study Visit 4 Day 112 +/- 14 day
Procedures					
Informed consent	X				
SCID-5	X				
WRAT-4	X				
Demographics		X			
Medical history		X			
BACS		X			
VRFCAT		X			
MINI		X			
PSQI		X			
WHODAS 2.0		X			
PHQ-9		x			
PANSS		X	X	X	X
Calgary Depression Scale (CDSS)		X	X	X	X
Treatment Rationale Scale		X	X	X	X
CSSR-S		X	X	X	X
IA on METER and VLMT		X	X	X	X
Metacognitive WCST		X	X	X	X
Informant-Rated SLOF		X			X
GPS			X	X	X
Compensatory Cognitive Strategies Scale (Informant)		X			X
CAINS Motivation		X	X	X	X
Defeatist Performance Beliefs		X	X	X	X
Client Satisfaction Questionnaire (CSQ)		X	X	X	X
Negative Effects			X	X	X
Trials and Coaching Sessions Completed			X	X	X
HVLT			X	X	X
Metacog ER-40			X	X	X
Brief Regulation of Motivation Scale			X	X	X
Karolinska Sleepiness Scale			X	X	X
GAD-7			X	X	X

2 INTRODUCTION

Leave blank. Text should be included under the relevant subheadings below.

2.1 STUDY RATIONALE

Psychotic disorders are among the most disabling illnesses in the world¹, yet trials of cognitive training and related rehabilitative interventions have struggled to demonstrate durable impact on functional outcomes^{2,3}. In part, this is due to a common target focus on cognitive capacity or first-order ability, which predicts no more than 20% of variation in functional outcome⁴. Introspective accuracy (IA), i.e., second-order judgements of one's abilities as compared to objective evidence, accounts for substantial variability in functional outcome independent from capacity^{5,6,7}. As such, IA is a potential intervention target for functioning, but no interventions have directly and experimentally targeted IA in psychotic disorders using any format. This Experimental Therapeutics project tests a new blended digital health intervention called Improving Thinking through Everyday Self-Assessment Training (iTEST) that targets IA to ultimately improve functioning.

2.2 BACKGROUND

Schizophrenia and schizoaffective disorder, referred to hereafter as *psychotic disorders*, affect 1.5% of the population and cause the most substantial disability, greatest associated healthcare and indirect costs per person affected of any psychiatric disorder^{1,11,12}. Over the past 20 years, a large body of clinical trials have evaluated interventions with cognitive capacity as a focal target for reducing this disability, including large scale NIMH-led efforts such as MATRCS¹³, TURNS¹⁴, and drug and behavioral trials¹⁵. To date, therapeutic impact on everyday functioning has been modest at best. A 2019 meta-analysis of 24 studies of drill-and-practice cognitive training found improved cognition but no impact on function³. Cognitive remediation interventions have much larger effects on functioning, but are intensive (35+ hours training), and the impact on function may not be durable^{9,16-17}. Metacognitive components are important for transfer to change in function¹⁸, but are not a focus of experimentation¹⁹, and so a key need is for experimentally tested efficient treatments targeting mechanisms underlying metacognition impairments for durable functional improvement^{20,21}.

A growing body of literature spanning cognitive science, education, and more recently, psychiatry, has associated inaccurate judgements of performance, or poor Introspective Accuracy (IA), with poor functioning. We define IA as the discrepancy between objective data and subjective estimation of task performance, ability, or behavior^{5,22}. Our published work and that of others has identified the following: 1) Poor IA is Predictive of Poor Functioning: Poor IA, as measured by greater discrepancies between actual and judged performance, accounts for up to 42% of the variance in disability in social and nonsocial functional domains²³⁻²⁶; 2) IA is Independently Associated with Functioning Beyond Capacity: The contribution of IA to disability is independent from that associated with actual cognitive and social cognitive performance, and the relationship between cognition and functioning is minimal (~3% of variance)^{27,28} once IA is accounted for; 3) IA Impairments are Worse in Psychotic Disorders vs. Other Conditions: In contrast to bipolar disorder, people with psychotic disorders produce judgements that are not correlated with actual performance despite contemporaneous feedback²⁹, indicating substantial disruption in self-assessment processes; 4) IA Impairments are Conserved across Domains and

Measurement Modalities: Discrepancies between self-assessments and informant reports of functioning are associated with task-based IA deficits^{5,23}. In each of these studies, participant self-assessment was poorly linked to objective data even with performance feedback (e.g. task feedback³⁰; objective data regarding vocational outcomes^{28,31})

In contrast to psychiatric research, interventions targeting performance judgments are an active domain of cognitive science and education research in healthy adults. In a recent study, an experimental IA training intervention in healthy adults improved IA on a trained task as well as transfer of training to IA for a novel task¹⁰. In that intervention, adults were trained by repeated immediate feedback on the accuracy of their performance judgments on a signal detection paradigm, over the course of 8 weeks. The control condition received feedback regarding their performance but not on the accuracy of their self-ratings (i.e., IA). This intervention was self-directed and computerized, in aggregate accounting for only 8 hours of exposure. The active condition improved IA, and that improvement transferred to a novel task, whereas no such effects were evident in the control condition. As such, a targeted computerized drill-and-practice intervention could improve IA with generalization to IA on other tasks. Related experimental work in the educational literature indicates that improvement of task-based judgments of performance has a strong impact on learning^{50,51}, which has recently been extended to functional pursuits like employment searches^{52,53} (again in healthy adults). To be impactful in a clinical population, a key consideration is distal transfer to functioning⁵⁴. In experimental studies, poor IA is related to reduced use of compensatory strategies like reminders⁵⁵, as well as increasing risk for failure experiences when real-world tasks are attempted⁵⁶. Thus, without training in IA, use of compensatory strategies may be low and chances of failure may increase. Given the potential pitfalls in distal transfer for translational interventions⁵⁷, iTEST's task-based training for cognitive IA is directly coupled with improving global judgements of actual behavior measured by EMA (i.e., IA for functional activity). Further, iTEST coaching centers on connecting IA training to use of compensatory strategies (e.g., calendaring, reminders) for achieving personalized goals. Thus, iTEST would be the first intervention of any kind to target IA in psychotic disorders, and would also be the first intervention to target IA using a blended mobile intervention format for any condition.

Although computerized IA training could occur in a lab-based setting, there are several advantages to a remote "virtual first" development strategy⁵⁹. The need for and practicality of clinic-based training has diminished with the emergence of telehealth, and mobile interventions could increase access and reduce transportation costs⁶⁰. Mobile interventions that require daily/several times per day interventions are acceptable, feasible, and effective in psychotic disorders, as our group⁶¹⁻⁶³ and others⁶⁴⁻⁶⁷ have shown. Given the shift to telehealth, interventions may benefit from initial deployment in a remote format (rather than post-development adaptation). In addition, employing mobile devices as a platform for iTEST, a potentially transformative approach is that we can also link judgements of task performance to contemporaneous information (time and place, and social context) of real-time behavior, directly transferring IA on cognitive tasks to improved accuracy for judgements of actual engagement in functional activity.

iTEST's design incorporates recommended elements (e.g., human involvement, personalization) of cognitive remediation from a consensus panel⁸. That panel included experts in cognitive remediation and created a published consensus document called a white paper that detailed what the recommended ingredients of cognitive remediation for psychotic disorders should include, focusing on increasing adherence and potential impact. Yet, iTEST does not involve broad capacity-building activities. As such, the intensity of iTEST amounts to ~50% of the average contact time of cognitive remediation, which, if effective in improving function, would yield a favorable acceptability and scalability profile. The Task-based components of iTEST build upon our validated Mobile Variable Difficulty List Memory Test [VLMT]⁹ and Mobile Electronic Test of Emotional Recognition (METER)¹⁰, each of which includes IA judgements of performance and together target IA for two different cognitive domains (verbal learning and facial emotion recognition).

[figure not shown]

Figure 1. Selected Screen Shots of iTEST (Alpha Version)

During each VLMT and Meter administration, participants are presented with 3 trials where lists of words or faces are presented. For the VLMT, immediately following each exposure to the list, participants were shown target and recognition foil words one-by-one and asked to indicate whether or not the word appeared on the list. For the METER task, participants are asked to guess the emotion in a picture of a human face from **among anger, sadness, happiness, no emotion, or fear**. **After completion of the task, scoring includes the** percentage of correct identifications of target words or faces per trial. In embedded validity tests, after each administration, participants self-reported if they were distracted or interrupted.

These tasks are an ideal foundation for iTEST since they are proven to be acceptable, correlated with in-lab performance on tests of the same construct in people with psychotic disorders^{9,10}, and associated with functional outcome¹¹. In addition, there were no practice effects or changes in IA associated with repeated testing either task, so administration of the tasks alone does not alter task performance or IA. The iTEST intervention contains brief (~15 min) Task-based IA training delivered 6 days per week on the individual's mobile device to improve accuracy of task-level and global judgments of performance. Training uses gamified adaptation of both the VLMT and METER to improve IA in two separate, but critical functional domains – memory and social cognition, thus broadening potential impact. Training is graduated, such that initial stages focus on engaging attention on the parameters of the task, then formation of global judgements based on trial-level feedback (rather than self-generated information) for both memory and social cognitive domains. In so doing, increased and continuous attention to external feedback (vs. self-generated information) is shaped. Individual Coaching is coupled with the task-based IA remote training and includes psychoeducation in how IA problems impact function and training in use of compensatory strategies (e.g., reminders, calendaring, asking others how they are feeling) to apply to everyday cognitive and social cognitive demands that are linked to individualized personal goals. Two rounds of alpha-testing of iTEST have been completed.

Since iTEST is the first intervention to target IA in psychotic disorders, and the first blended intervention to target IA in any condition, the scope of this research is a pilot trial. The goal of the R61 phase and this protocol is to evaluate whether iTEST can substantially improve IA and is associated with acceptable adherence.

2.3 RISK/BENEFIT ASSESSMENT

Leave blank. Text should be included under the relevant subheadings below.

2.3.1 KNOWN POTENTIAL RISKS

Assessment: Participation in the evaluation and responding to questions on the mobile device requires time and attention. Some participants may become bored or fatigued completing the evaluation. Some participants may also become distressed during the psychiatric evaluation, which requires them to discuss their current symptoms, as well as history of their symptoms.

Intervention: Although the blended computerized interventions to be tested in this study are not expected to produce adverse reactions, participants may become bored or fatigued with the intervention procedures. There is a theoretical possibility that improvements in introspective accuracy may engender increases in depression alongside greater awareness of limitations.

Disclosure or Identification of Suicidal Ideation or Intent Harm Self: During structured interviews concerning suicide (via the Columbia Suicide Severity Scale¹² or CSSR-S) or extemporaneous discussion with rater or other staff, participants may disclose a level of risk of harming themselves or others that would require an evaluation for a higher level of care.

Confidentiality/Loss of Privacy: As with any clinical research study, a risk of disclosure of personal material exists. These risks are present in interview and scale-based measures and technology-based data collection.

2.3.2 KNOWN POTENTIAL BENEFITS

Participants may benefit from participating in the experimental intervention by learning skills to improve introspective accuracy and may also experience, based on study hypotheses, improvements in functioning.

2.3.3 ASSESSMENT OF POTENTIAL RISKS AND BENEFITS

The risks and potential adverse effects associated with this research are minimal. We judge the importance of knowledge resulting from this study and the potential for improving functioning among people with psychotic disorders to be quite significant; therefore, the risk to benefit ratio is low.

3 OBJECTIVES AND ENDPOINTS

In this pilot project, there are two objectives. Firstly, we will evaluate, in an open trial, whether iTEST is acceptable, indexed by adherence, and engages IA as a target, indexed by improved IA on trained

tasks and transfer on an untrained task in a different domain. Secondly, we will evaluate optimal dosing of the intervention, by whether go/no-go criterion for improvement is achieved at 8, 12, or 16 weeks.

Our go/no go criteria are threefold: 1) To demonstrate feasibility, the average adherence must be equal to or exceed 75%, 2) To show target engagement, we require a significant improvement in IA ($d > .50$) on both trained tasks, and 3) To show transfer of training, we require significant improvement in IA ($d > .50$) on the untrained Wisconsin Card Sorting Task. Criteria may be met prior to 16 weeks, at weeks 8 or 12 (Note: all participants continue through 16 weeks).

OBJECTIVES	ENDPOINTS	JUSTIFICATION FOR ENDPOINTS
Primary		
To evaluate the acceptability and preliminary impact on our target, IA	
Adherence defined as the ratio of completed mobile prompts completed divided by the number possible – 75% is the criterion
 
Clinically significant (Cohen's $d > 0.5$) improvement in trained introspective accuracy as measured by IA on our Verbal Learning and Memory Test and Mobile Electronic Test of Emotion Recognition tasks. These are administered 6x per week for 16 weeks.
 
Clinically significant (Cohen's $d > 0.5$) improvement in untrained introspective accuracy (global resolution score) on the WCST. The WCST is administered at baseline, 8, 12 and 16 weeks.
	
Adherence at a level of 75% is generally accepted in mobile intervention studies such as this
 
The reason that trained tasks are part of our Go/No Go criteria is because lack of improvement on trained tasks would call into question the ability of iTEST to modify IA, and would indicate need for program revisions. IA is calculated as the discrepancy (absolute) between each trial's correct performance from that estimated by the participant, which is nested within sessions and weeks.
 
An additional Go/No Go component is transfer of training to an untrained task-based measure of IA, the Meta-Cognitive Wisconsin Card Sorting Test¹³. IA on this task is also associated with functioning and improvement on this task would support that iTEST

OBJECTIVES	ENDPOINTS	JUSTIFICATION FOR ENDPOINTS
		leads to generalized improvement in IA.
Secondary		
To identify the briefest duration of iTest that in which the sample reaches criterion	Reaching Criterion at 8, 12, or 16 weeks	Our rationale for the dosing framework is as follows. Our starting dose is that in-lab IA intervention in healthy adults occurred over 8 weeks and included 2160 total trials and 80 instances of IA feedback (in aggregate ~6 hours) ¹⁴ . iTEST at 8 weeks equates to 4320 trials and 188 rounds of feedback (8-10 hours), which is about 2 times the dose of the in-person IA intervention in healthy adults ¹⁴ . We will then extend this period to 16 weeks with additional evaluations at 12 and 16 weeks, yielding a maximum of 16-20 hours of training in aggregate.
Tertiary/Exploratory		
To evaluate the impact of iTEST on functional impairment	The informant-rated Specific Level of Function (SLOF) scale will be used to measure functional outcome ¹⁵ . The SLOF is a 43-item interview administered as informant- or self-report. The scale assesses the participant's current functioning integrated into a single higher-order factor ¹⁶ integrating social, everyday, and vocational activities.	The SLOF emerged as the most reliable and externally valid scale-based measure of functioning in the team's prior validation study ¹⁷ . Informants ratings on the SLOF were also found to be sensitive to short term functional gains (12-24 weeks) in a treatment study ¹⁸ .

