9 STATISTICAL CONSIDERATIONS

9.1 STATISTICAL HYPOTHESES

The statistical hypotheses are that adherence will exceed the criterion of 75% and that there will be a pre-post change in the VLMT, METER and WCST tasks that will exceed that of 0.5 Cohen’s d with the baseline sample wide standard deviation serving as the denominator.

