9.2 SAMPLE SIZE DETERMINATION

We used the Monte Carlo simulation capabilities of Mplus version 8.4⁵² to perform our power analyses. To determine our levels of power to detect changes in IA for the list-learning task or emotion recognition tasks equivalent to $d = |0.50|$ for R61 Aim 1, we specified three-level models with 1000 replications each wherein trials ($t = 18$) were nested within weeks ($w = 8, 12, \text{ or } 16$) that were further nested within persons ($n = 60$ or 48 in the case of 20% attrition). These models were similar to Figure 1 with the exception that changes in IB and IA at Level 3 were not regressed on intervention condition. As can be seen in Table 1, our power levels were excellent (i.e., $> .90$) across all combinations of sample size and week size, ranging from .91 for detecting changes in IA of $d = -0.50$ at 8 weeks with 48 participants to .97 for detecting changes in IA of $d = 0.50$ at 16 weeks with 60 participants.

To determine our levels of power to detect transfer-of-training for R61 Aim 1 and optimal dosing for Aim 2, we again specified three-level models with 1000 replications each wherein trials ($t = 18$) were nested within weeks ($w = 8, 12, \text{ or } 16$) that were further nested within persons ($n = 60$ or 48 in the case of 20% attrition). However, we modified these models such that they included an additional Truth and Bias model for the WCST transfer of training target at Level 2 that had a change in IB of $d = -0.50$ across the weeks. To reflect the fact that this in-laboratory tasks would only be measured at 0, 4, 8, 12, and 16 weeks, we specified that these measurements should have 62.5% missing data in the simulations (e.g., only completing 3 out of 8 weeks). As can be seen in Table 2, we should have more-or-less adequate levels of power to detect a change in IB for the in-lab assessment at 16 weeks with 48 participants (power = .77) and adequate power to detect a change in IB for the in-lab assessment at 12 and 16 weeks with 60 participants (power = .78 and .83, respectively).

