9.4 STATISTICAL ANALYSES

9.4.1 GENERAL APPROACH

[figure not shown]
As this is a pilot study, there is no formal SAP

Since our analyses focus on clinically significant magnitude of effects or achievement of thresholds, significance testing is not relevant

We will use Multilevel Structural Equation Modeling (MLSEM) with three levels to estimate changes in levels of Introspective Accuracy (IA) across trials (level 1) and/or weeks (level 2) within persons (level 3). Figure 1 presents an example three-level model wherein changes in IA for the *Variable Length Memory Test* (VLMT) list learning and *Mobile Electronic Test of Emotion Recognition* (METER) emotion recognition are simultaneously estimated. Given the relatively large number of random effects, we will use Bayesian

estimation rather than maximum likelihood estimation for the analyses⁵³. Although some task or ability domains will not be measured at every trial or every week, specifying trial as Level 1 (e.g., for IA on mobile task) and week as Level 2 (e.g., for WCST) will still enable us to estimate changes in IA for these domains.

Figure 1. Three-Level Multilevel Structural Equation Model

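### The go criteria ask for significance that the plan will not test; the working rule is an estimated d above 0.5, and the stated power is not the chance of meeting it

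*Combined protocol and SAP*

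**What the plan says.** - **Section 3, go/no-go text.** For VLMT and METER: "we require a significant improvement in IA ($d > .50$) on both trained tasks". For transfer: "we require significant improvement in IA ($d > .50$) on the untrained Wisconsin Card Sorting Task".
- **Section 3, endpoint table.** The trained-task endpoint is "Clinically significant (Cohen's $d > 0.5$) improvement in trained introspective accuracy", and the WCST row uses the same wording.
- **Section 9.1.** The hypothesis is that "there will be a pre-post change in the VLMT, METER and WCST tasks that will exceed that of 0.5" in Cohen's d units, "with the baseline sample wide standard deviation serving as the denominator".
- **Section 9.2.** Power for R61 Aim 1 comes from simulation at d = 0.50. For trained IA, "our power levels were excellent (i.e., $> .90$) across all combinations of sample size and week size", from .91 (n=48, 8 weeks) to .97 (n=60, 16 weeks). For the WCST the text gives .77 (n=48, 16 weeks), .78 (n=60, 12 weeks) and .83 (n=60, 16 weeks), each for a change in IB.
- **Section 9.4.1.** There is no formal SAP. "Since our analyses focus on clinically significant magnitude of effects or achievement of thresholds, significance testing is not relevant". Estimation is Bayesian, and Aim 1 is judged by looking at the standardised differences at weeks 8, 12 and 16.
- **Section 9.4.3.** The dose question is which of those weeks reaches d = 0.5.

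No alpha, sidedness, credible level or posterior-probability rule is stated anywhere.

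**The concern.** Two things do not fit together. First, the go criteria use the word significant, while the analysis section sets significance testing aside. Second, the sample size rests on power, which is a property of a test, while the decision rests on whether an estimate crosses 0.5. A reader of Section 9.2 would take .91 to .97 as roughly the chance of satisfying the trained-task criterion if iTEST works as designed. It is not.

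The rule matters because it decides whether the R33 trial goes ahead and which duration it uses. If its operating characteristics are not written down, a go from a bare crossing of 0.5 can be taken as evidence that the true effect exceeds 0.5, and a no-go can be taken as failure when the true effect was exactly the one planned for.

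**Working it through.** **1. What the stated power corresponds to.** The variance components and alpha of the Mplus simulation are not given, so it cannot be rebuilt. As a check, take a paired t-test of zero change, two-sided 5% (assumed), with the SD of change equal to the baseline SD (pre-post correlation 0.5, assumed). The non-centrality is 0.5 × √n.

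- n=60: 0.5 × √60 = 3.873, power .968 (stated: .97).
- n=48: 0.5 × √48 = 3.464, power .924 (stated: .91).

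This is close but not exact. It ignores trials and weeks, and it does not give the WCST figures. One-sided 5% gives .985 and .962, which fits less well. The trained-task figures are therefore consistent with a two-sided 5% test against zero.

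**2. Standard errors implied by the stated power.** Under the same assumed test, SE = 0.5 / (1.96 + z_power).

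| Stated power | z_power | SE of d | Estimate needed for significance against 0 (1.96 × SE) |
|---|---|---|---|
| .97 (trained, n=60) | 1.881 | 0.130 | 0.255 |
| .91 (trained, n=48) | 1.341 | 0.152 | 0.297 |
| .83 (WCST IB, n=60, 16 weeks) | 0.954 | 0.172 | 0.336 |
| .78 (WCST IB, n=60, 12 weeks) | 0.772 | 0.183 | 0.359 |
| .77 (WCST IB, n=48, 16 weeks) | 0.739 | 0.185 | 0.363 |

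Every hurdle in the last column is below 0.5. Adding a test against zero to the rule would change no decision for an estimate above 0.5.

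**3. Chance of passing one task under the working rule.** For an unbiased, roughly normal estimate, P(estimate > 0.5) = Φ((δ − 0.5) / SE), where δ is the true effect. At δ = 0.5 this is Φ(0) = 0.50. The SE cancels, so neither sample size nor repeated trials can raise it.

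**4. Chance of passing all three at δ = 0.5.** For three equally correlated normal estimates this is 1/8 + (3 / 4π) × arcsin(ρ):

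- ρ = 0: 0.125
- ρ = 0.5: 0.125 + 0.2387 × 0.5236 = 0.250
- ρ = 0.8: 0.125 + 0.2387 × 0.9273 = 0.346

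**5. Other true effects.** n=60, same δ on all three tasks, SE = 1/√60 = 0.129 for trained tasks and 0.172 for the WCST, trivariate normal:

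| True d | Each trained task | WCST | All three, ρ = 0.5 (ρ = 0 to 0.8) |
|---|---|---|---|
| 0.5 | 50% | 50% | 25% (12–35%) |
| 0.6 | 78% | 72% | 55% (44–63%) |
| 0.8 | 99% | 96% | 95% (94–96%) |

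**6. Passing when the criterion is truly unmet.** With WCST δ = 0.4 and SE 0.172: 1 − Φ(0.1 / 0.172) = 1 − Φ(0.58) = 28%.

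All of these figures are for a single assessment week and leave out the adherence criterion.

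**The case against.** The strongest reply is that the documents already define the term as a magnitude. The endpoint table attaches clinical significance to the same threshold on the same tasks, Section 9.4.1 gives magnitude and thresholds as its reason for setting tests aside, and Section 9.4.3 asks only which week reaches 0.5. On that view one sentence lacks the word clinically and nothing else is wrong. The reply is right about the rule, and this point adopts that reading.

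A reader might infer something stronger: that significant beside d > .50, together with the Section 9.1 hypothesis, requires evidence that d is above 0.5, so that at an assumed two-sided 5% level estimates between 0.5 and roughly 0.75 to 0.86 would be a go under one statement and a no-go under another. The documents do not support this. No lower bound or null value of 0.5 appears. Section 9.1 uses the same verb for adherence, which Section 3 applies as a simple average against 75%. Under such a rule the power at d = 0.5 would be 2.5%, not the values in Section 9.2.

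It can also be said that this is a single-arm pilot and that power against zero is a conventional way to size one. That is fair, but it leaves Section 9.2 describing a test that Section 9.4.1 sets aside, for an aim decided in another way.

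**Conclusion.** The point holds as an inconsistency of wording and a mismatch between the sample-size justification and the decision rule, not as two rules that give opposite decisions. Stated power of .91 to .97 and .77 to .83 sits beside a pass probability of about 50% per task and about 25% for all three at the same design effect. The WCST powers, moreover, are stated for IB, whereas the criterion concerns IA.

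The 50% figure needs only an unbiased, symmetric estimate; informative priors, which are not described, could move it. The joint figures also need the between-task correlation, shown from 0 to 0.8. The figures away from d = 0.5, including the 28%, rest on the assumed two-sided 5% test and, for the trained tasks, on a pre-post correlation of 0.5. Because Section 3 lets the criteria be met at week 8, 12 or 16, the chance of passing at some week would be higher than at one week, by an amount the documents do not allow to be computed; the adherence criterion works the other way.

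**What to change.** 1. In the Section 3 go criteria, write clinically significant and define it as a posterior point estimate of d above 0.5 (naming mean or median). Use the same rule in Sections 9.1 and 9.4.1, and say that no test against 0.5 is made.
2. In Section 9.2, state that the power is for detecting a non-zero change, with its alpha and sidedness, and that it is not the probability of a go. Add the probability of meeting the go rule, per task and jointly, over a range of true d, from the existing simulation models.
3. In Section 9.4.1, plan to report for each task the 95% credible interval and P(d > 0.5), with the joint probability for all three. A bare crossing should be reported as the criterion met with that uncertainty, not as improvement above 0.5 having been shown.

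The cost is wording in four sections and one more summary of the simulations. The intervals and probabilities come from the Bayesian fit already planned, with no new data, visits or participants. The downside is small: a borderline go will carry a modest posterior probability, and the stated operating characteristics will look less favourable. The change should be made before outcome data are inspected.
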